7.6.5 Methods for evaluation of measurable disease

All measurements should be taken and recorded in metric notation using a ruler or calipers. All baseline evaluations should be performed as closely as possible to the beginning of treatment and never more than 6 weeks before the beginning of the treatment.

The same method of assessment and the same technique should be used to characterize each identified and reported lesion at baseline and during follow-up. Imaging-based evaluation is preferred to evaluation by clinical examination unless the lesion(s) being followed cannot be imaged but are assessable by clinical exam.

Clinical lesions. Clinical lesions will only be considered measurable when they are superficial (e.g., skin nodules and palpable lymph nodes) and ≥ 10 mm diameter as assessed using calipers (e.g., skin nodules). In the case of skin lesions, documentation by color photography, including a ruler to estimate the size of the lesion, is recommended.

Chest x-ray. Lesions on chest x-ray are acceptable as measurable lesions when they are clearly defined and surrounded by aerated lung. However, CT is preferable.

Conventional CT and MRI. This guideline has defined measurability of lesions on CT scan based on the assumption that CT slice thickness is 5 mm or less. If CT scans have slice thickness greater than 5 mm, the minimum size for a measurable lesion should be twice the slice thickness. MRI is also acceptable in certain situations (e.g., for body scans).

Use of MRI remains a complex issue. MRI has excellent contrast, spatial, and temporal resolution; however, there are many image acquisition variables involved in MRI, which greatly impact image quality, lesion conspicuity, and measurement. Furthermore, the availability of MRI is variable globally. As with CT, if an MRI is performed, the technical specifications of the scanning sequences used should be optimized for the evaluation of the type and site of disease. Furthermore, as with CT, the modality used at follow-up should be the same as was used at baseline and the lesions should be measured/assessed on the same pulse sequence. It is beyond the scope of the RECIST guidelines to prescribe specific MRI pulse sequence parameters for all scanners, body parts, and diseases. Ideally, the same type of scanner should be used and the image acquisition protocol should be followed as closely as possible to prior scans. Body scans should be performed with breath-hold scanning techniques, if possible.

7.6.6 Methods of evaluation of bone disease

Bone disease will be evaluated using Radionuclide bone scan.

7.6.7 Progression/response criteria

Non-lethal disease progression (necessitating discontinuation from trial) is either clinical progression (see Section 7.6.7.5) or radiographic progression based on RECIST (see Section 7.6.7.1, 7.6.7.2) or PCWG3 bone scan criteria (see Section 7.6.7.4). These are combined and

shown in graphical format in Section 7.6.8. Confirmatory bone scan ≥ 4 weeks after first bone scan progression per PCWG3 is required and must show ≥ 2 new lesions.

PSA progression alone is NOT sufficient for removal from study.

7.6.7.1 Evaluation of target lesions

Complete Response (CR): Disappearance of all target lesions. Any pathological lymph nodes (whether target or non-target) must have reduction in short axis to <10 mm.

Partial Response (PR): At least a 30% decrease in the sum of the diameters of target lesions, taking as reference the baseline sum diameters.

Progressive Disease (PD): At least a 20% increase in the sum of the diameters of target lesions, taking as reference the smallest sum on study (this includes the baseline sum if that is the smallest on study). In addition to the relative increase of 20%, the sum must also demonstrate an absolute increase of at least 5 mm. (Note: the appearance of one or more new lesions is considered progression).

Stable Disease (SD): Neither sufficient shrinkage to qualify for PR nor sufficient increase to qualify for PD, taking as reference the smallest sum diameters while on study.

7.6.7.2 Evaluation of non-target lesions

Complete Response (CR): Disappearance of all non-target lesions and normalization of tumor marker level. All lymph nodes must be non-pathological in size (<10 mm short axis).

Note: If tumor markers are initially above the upper normal limit, they must normalize for a patient to be considered in complete clinical response.

Non-CR/Non-PD: Persistence of one or more non-target lesion(s) and/or maintenance of tumor marker level above the normal limits.

Progressive Disease (PD): Appearance of one or more new lesions and/or unequivocal progression of existing non-target lesions. Unequivocal progression should not normally trump target lesion status. It must be representative of overall disease status change, not a single lesion increase.

Although a clear progression of “non-target” lesions only is exceptional, the opinion of the treating physician should prevail in such circumstances, and the progression status should be

confirmed at a later time by the review panel (or Principal Investigator).

7.6.7.3 Outcomes based on radionuclide bone scans

The subjectivity in interpreting serial changes in a radionuclide bone scan is well recognized. Thus, the primary outcome will be whether the scan is stable or improved, vs. worse or progression. Changes in intensity will not be used as an outcome measure.

Stable or Improved: A stable or improved classification requires that no new lesions appear at the 3rd cycle (12 weeks) \pm 1 week assessments.

Progression (Non-Response): Appearance of **two or more** new skeletal lesions. *An increase in the size or intensity of known skeletal lesions will not be considered progression.* This must be confirmed with another bone scan \geq 4 weeks after first bone scan progression per PCWG3 and must show \geq 2 new lesions.

7.6.7.4 Outcomes based on post-therapy PSA changes

These definitions are intended to characterize the PSA changes on study for the purpose of reporting of results. PSA progression is NOT criteria to remove from study.

Complete Response (CR): Undetectable PSA (\leq 0.2 ng/ml) that is confirmed by another PSA level at no less than 4 weeks interval.

Partial Response (PR): Decrease in PSA value by \geq 50% that is confirmed by another PSA level at no less than 4 weeks interval.

Stabilization (SD): Patients who do not meet the criteria for PR or PD for at least 90 days on study (2 cycles of treatment) will be considered stable

Progression (PD): 25% increase over baseline or nadir whichever is lower and an increase in the absolute value of PSA level by 2 ng/ml that is confirmed by another PSA level at no less than 4 weeks interval.

7.6.7.5 Definition of progression based on pain

Progression by pain criteria is based on pain due to prostate cancer requiring one or more of the following palliative interventions:

- Opioid Therapy: Intravenous, intramuscular or subcutaneous opioid therapy administered as a single dose; oral or transdermal opioid analgesic use administered for 10 out of 14 consecutive days, and/or requiring Radionuclide or Radiation therapy.
- Evidence of disease at the site of pain is required. Pain requiring only non-opioid analgesics will not be considered disease progression.

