2.2 Secondary Objectives

Secondary Objective:	Outcome Measure:
To determine the response rate of the combination of olaparib and AZD6738 in mCRPC patients who are DNA repair deficient (mono- or biallelic somatic ATM loss OR biallelic somatic loss of BRCA1 or BRCA2 OR known mono or biallelic germline loss of ATM, BRCA1, or BRCA2).	The rate of response (CR/PR) per radiographic response according to RECIST v1.1 or PSA ($\geq 50\%$ decline) in DRDef patients.
All of the below secondary objectives will be calculated for the DRPro, DRDef patients separately.	
Objective progression-free survival (combined radiographic and clinical progression-free survival)	The objective progression-free survival is the duration of time from start of treatment to date of progression (based only on radiographic progression or clinical decline/death).
Objective radiographic disease response rate	The rate of achieving a radiographic response according to RECIST v1.1.
PSA progression-free survival	Composite of survival and duration of PSA control as defined by time from start of therapy to first PSA increase $\geq 25\%$ and ≥ 2 ng/ml above the nadir and confirmed by a second value at or beyond 4 weeks later.
PSA response rate for ≤ 0.2 ng/ml, 50% decline, 90% decline from entry PSA and confirmed 4 weeks later	The rate of achieving the aforementioned PSA value or percent decline compared to PSA at entry.
Duration of combined radiographic and PSA response	Time from first documented response (RECIST v1.1 CR/PR or PSA decline $\geq 50\%$) until death, recurrent or progressive disease (based on RECIST v1.1) or first PSA increase $\geq 25\%$ and ≥ 2 ng/ml above the PSA nadir.

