5. STUDY CALENDAR

	Screening (Day -42 to Day -1)	Cycle 1 ^m , 2 ^m		Cycle 3+ Day 1 ^m (-5 to +3d)	End of Treatment, 30 (±3) Day FU ^m	Long- term FU ^j
		Day 1 ^m (±3day for c2)	Day 8 ^m (±3 day)			
Informed Consent	X					
Medical/Surgical History, Demographics, Height Prior Histology (either report or clinician note as source)	X					
Biopsy of Metastatic Disease	X ^a					
Peripheral blood for germline and/or circulating tumor DNA	X ^b					
PE, Vitals ⁱ , Weight	X	X ^m	X ^m	X ^m	X ^m	
Performance Status	X	X	X	X	X	
Adverse Event, Toxicity Evaluations		X	X	X	X	
Medication Review	X	X	X	X	X	
Study Drug ^c		X	X	X		
Radiologic evaluations and measurements ^d	X (Must be ≤4 weeks from C1D1 or repeated) ^k			X ^e		
ECG	X (triplicate)	X ^g (C1D1 only)				
Serum Chemistry ^f , LDH	X	X	X (optional C2D8)	X	X	
PT (INR), APTT, Urinalysis ^h	X					
CBC with Differential	X	X	X (optional C2D8)	X	X	
PSA	X	X		X	X	

	Screening (Day -42 to Day -1)	Cycle 1 ^m , 2 ^m		Cycle 3+ Day 1 ^m (-5 to +3d)	End of Treatment, 30 (±3) Day FUm	Long- term FU ⁱ
		Day 1 ^m (±3day for c2)	Day 8 ^m (±3 day)			
Testosterone	X					
Circulating Correlatives		X ⁿ		C3D1 only ⁿ	X ⁿ	
Long-term follow- up for MDS/AML or new primary malignancy reporting						X

a. Biopsy must be done after patient has consented and registered to the study (unless pre-existing, CLIA certified lab, next-generation sequencing of metastatic mCRPC biopsy has been completed or mCRPC tissue available to submit for testing). Submitted tissue must be deemed adequate or fully reported prior to starting therapy.

b. Peripheral blood is sent for either germline comparison (if tissue also completed) or exploratory analysis of circulating tumor DNA and germline DNA if biopsy failed or is unsafe (and analysis available). If the biopsy is attempted and has insufficient tissue, new blood may not need to be redrawn as it was sent with biopsy.

c. For drug schedule see Section 1.2.

d. Radiographic evaluation will include radionuclide bone scan, CT or MRI of abdomen and pelvis, and CT, CXR or MRI of the chest as appropriate. All disease sites must be assessed using the same methodology as performed at baseline. At the discretion of the investigator, additional radiological evaluations may be performed at an unscheduled time point.

e. While receiving therapy, radiologic tests are performed every 8 weeks (±1 week) from C1D1. After the third scanning timepoint (~6 months), radiologic tests are performed every 12 weeks (±1 week) from C1D1.

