5.6 Discontinuation of Investigational Product

Subjects may be discontinued from protocol treatment in the following situations:

- Subject decision. The subject is at any time free to discontinue treatment, without prejudice to further treatment
- Adverse Event
- Severe non-compliance with the study protocol
- Bone marrow findings consistent with myelodysplastic syndrome (MDS)/acute myeloid leukemia (AML)
- Disease Progression (as defined by Section 7.6.7). In the absence of other indicators of disease progression, therapy should not be discontinued based on PSA rise alone.

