10.1.2 Analysis of the secondary endpoints

- The response rate and 95% binomial confidence interval will be reported for DRDef patients.

The following endpoints will be reported for DRDef and DRPro patients separately

- Objective progression-free survival (combined radiographic and clinical progression-free survival) will be reported using Kaplan-Meier methods. This is measured from the date of treatment arm assignment until the specified tumor progression (assigned at the earliest observed time). Patients whose disease has not progressed at follow-up will be censored at the date when the last tumor assessment determined a lack of progression.
- Objective radiographic disease response rate is determined by the proportion of patients with measurable disease that have a response (CR+PR) according to RECIST v1.1. The proportion of responders will be reported with the corresponding 95% binomial confidence interval.
- PSA progression-free survival (PSA-PFS) will be reported as the composite of survival and duration of PSA control as defined by after a start of therapy from baseline to time of first PSA increase $\geq 25\%$ and ≥ 2 ng/mL above the nadir and confirmed by a second value at or beyond 4 weeks later. Kaplan-Meier methods will be used to report PSA-PFS.

- PSA response rate (≤ 0.2 ng/ml, 50% decline, 90% decline) proportions will be reported with corresponding 95% binomial confidence intervals. A waterfall plot of the best PSA response decline will be reported.
- Evaluate the qualitative and quantitative AE summaries will be reported by DNA repair status and organized by body system, frequency of occurrence, intensity (e.g. severity grade) and causality or attribution. Counts and proportions will be included. Treatment exposure will be summarized for all patients, including dose administration, number of cycles, dose modifications or delays and duration of therapy. Categorical variables will be reported using counts and frequencies. Continuous variables will be summarized using means or medians with the appropriate measure of variability.
- Duration of combined radiographic and PSA response will be reported using Kaplan-Meier methods.

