List created using <http://dmd.aspetjournals.org/content/dmd/43/4/490.full.pdf>

Note: Although BCRP is involved in a number of clinically relevant DDIs, none of the cited inhibitors above is truly specific for this transporter

Drugs known to be substrates of CYP3A4 and/or CYP2B6, undertake appropriate monitoring if co-administration is necessary

AZD6738 is a potential inducer of CYP3A4 and CYP2B6. Therefore, caution should be applied with co administration of drugs that are either completely metabolized by CYP3A4 and/or CYP2B6, or that are substrates of CYP3A4 and/or CYP2B6 and also have a narrow therapeutic index. Investigators should be aware that the exposure of other drugs metabolized by CYP3A4 and/or CYP2B6 may be reduced.

Table 11: Drugs known to be metabolized by CYP3A4 and have a narrow therapeutic index**- may co-administer, monitor toxicity/levels more frequently if possible**

Alfentanil	Quinidine
Cyclosporine	Sirolimus
Dihydroergotamine	Tacrolimus
Ergotamine	Astemizole
Fentanyl	Cisapride
Pimozide	Terfenadine

Table 12: Drugs known to be metabolized by CYP2B6 and have a narrow therapeutic index

- may co-administer, monitor for toxicity and check levels more frequently if possible

Cyclophosphamide	methadone
Ifosfamide	methoxetamine
Efavirenz	nevirapine
Bupropion	propofol
Propofol	selegiline
Thiotepa	sertraline
Sorafenib	sorafenib
alfentanil	tamoxifen
ketamine	valproic acid

From Flockhart DA (2007). "Drug Interactions: Cytochrome P450 Drug Interaction Table". Indiana University School of Medicine

Drugs known to be substrates of OATP1B1 and BCRP, undertake appropriate monitoring if co-administration is necessary

AZD6738 is also an inhibitor of OATP1B1 and BCRP. Caution should be applied with co-administration of substrates of OATP1B1 and/or BCRP as AZD6738 may increase their exposure.

These lists are not intended to be exhaustive and appropriate medical judgment is required. Please contact AstraZeneca with any queries you have on this issue. Please refer to full prescribing information for all drugs prior to co-administration with AZD6738.

Table 13: Drugs known to be substrates of OATP1B1

- may co-administer, be aware of potential drug toxicity

Atorvastatin	Methotrexate
Fluvastatin	Rifampin
Lovastatin	Bosentan
Pitavastatin	Glyburide
Pravastatin	Repaglinide
Rosuvastatin	Valsartan
Simvastatin	Olmesartan
Ezemibe	Atrasentan

List created using <https://www.solvobiotech.com/transporters/OATP1B1>

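### The pain-progression rule has no baseline reference: read literally, an unchanged opioid becomes an objective-PFS event within about two weeks

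*Combined protocol and SAP*

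**What the plan says.** Section 7.6.7.5 defines progression by pain as prostate-cancer pain that requires a listed palliative intervention. The opioid triggers are one intravenous, intramuscular or subcutaneous dose, or "oral or transdermal opioid analgesic use administered for 10 out of 14 consecutive days, and/or requiring Radionuclide or Radiation therapy". Two qualifiers follow: there must be disease at the painful site, and non-opioid analgesics alone do not count.

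Section 7.6.7 gives the rule its consequences: "Non-lethal disease progression (necessitating discontinuation from trial) is either clinical progression", with a pointer to 7.6.7.5, or radiographic progression. Section 5.6 lists progression under 7.6.7 among the reasons for stopping treatment.

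Section 10.1.2 carries clinical progression into the endpoint: "Objective progression-free survival (combined radiographic and clinical progression-free survival) will be reported using Kaplan-Meier methods". Time runs from treatment-arm assignment "until the specified tumor progression (assigned at the earliest observed time"). The analysis is done separately in the DRPro and DRDef cohorts.

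The objectives tables (synopsis and Section 2.2) describe the same endpoint as "based only on radiographic progression or clinical decline/death".

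**The concern.** A progression rule should be one that a patient with unchanged disease cannot meet. The opioid trigger depends on current use, with no comparison to use before treatment. A man who enters on a stable daily opioid for a painful bone metastasis meets every stated condition once he has been on study long enough to accumulate 10 days of use.

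Two things are at stake. First, the plan supports two rules, a literal one and one based on decline, and the four centers could apply different ones. To the extent that the literal one is used, objective PFS falls for a reason unrelated to the treatment. Second, the same event meets the protocol's condition for taking a patient off the trial, although he has not worsened.

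**Working it through.** The plan gives no assumed PFS, event count or baseline opioid share, so there is no figure to reproduce. The check has two parts: the text, then an illustration of size.

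**1. Does any progression rule other than pain lack a reference?**

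| Rule | Section | Reference |
|---|---|---|
| RECIST target lesions | 7.6.7.1 | Smallest sum on study, baseline included |
| RECIST non-target lesions | 7.6.7.2 | New lesions or unequivocal worsening of existing ones |
| Bone scan | 7.6.7.3 | Two or more new lesions, confirmed at least 4 weeks later |
| PSA (reporting only) | 7.6.7.4 | Baseline or nadir, whichever is lower |
| Pain | 7.6.7.5 | None stated |

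**2. Does another section supply the missing reference?** Sections 4.1 and 4.2 contain no exclusion for opioid use or for pain at entry. The study calendar has a screening "Medication Review", but no section links it to 7.6.7.5. Section 7.6.7.6 refers to Section 10.1 for PFS, and 10.1.2 adds no pain or opioid baseline.

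**3. When would the event fall?** With daily use counted from the first treatment day, the tenth day of use is day 10 and the 14-day window closes on day 14. Section 10.1.2 dates the event at the earliest observation, so it falls at about day 10 to 14.

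**4. How large could the effect be? (Assumptions only.)** Let q be the share of patients entering on a qualifying opioid and a the share of them whom sites count as events. Neither is in the documents. If baseline use is unrelated to true progression, then after day 14

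S_obs(t) = (1 − q·a) × S(t).

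With a true S(t) of 50%:

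| | q = 10% | q = 20% | q = 30% |
|---|---|---|---|
| a = 0 (sites read the rule as worsening) | 50% | 50% | 50% |
| a = 0.5 | 47.5% | 45% | 42.5% |
| a = 1 (literal rule everywhere) | 45% | 40% | 35% |
| Early events if a = 1, of 35 DRPro | 3.5 | 7.0 | 10.5 |
| Early events if a = 1, of 12 DRDef | 1.2 | 2.4 | 3.6 |

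For example, at q = 20% and a = 1: (1 − 0.20) × 50% = 40%. At q = 0 there is no bias for any a.

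**5. What if opioid users truly progress faster?** Let s be PFS in non-users and h the hazard ratio for users. Solve (1 − q)s + q·s^h = 0.5; with a = 1 the observed value is (1 − q)s. For h = 1.5 this gives 46.3%, 42.3% and 38.0%; for h = 2 it gives 47.2%, 44.0% and 40.1%. The bias shrinks but stays downward.

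**The case against.** The strongest reply is that the plan already signals worsening. The objectives limit the endpoint to progression seen radiographically or as clinical decline or death, and a stable opioid dose is not decline. The word progression points the same way, and many investigators would not enroll a man on stable analgesia only to call him progressed two weeks later. This stands as evidence of intent, and it is why zero bias is a real possibility. It does not remove the gap, because 7.6.7.5 is the operative definition, it omits the condition, and no section says which wording governs.

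It is also fair that objective PFS is a descriptive Kaplan-Meier endpoint in a non-comparative trial, and that Section 5.6 says patients may be discontinued, which is softer than 7.6.7. Both limit the consequence.

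A reader might infer three stronger points that the documents do not support.

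- **That Appendix B shows opioid users were expected.** Fentanyl and methadone appear in Tables 11 and 12 among drugs that may be given together with AZD6738 (Table 11: "may co-administer, monitor toxicity/levels more frequently if possible"). These are generic interaction lists. Table 12 also names cyclophosphamide and tamoxifen, although Section 4.3.2 bars other chemotherapy and hormonal therapy. The argument rests on the silence of 4.1 and 4.2 alone.
- **That the radiation wording contradicts itself.** Section 4.3.2 allows palliative radiotherapy for symptom control, which is wider than pain, and 5.4.13 deals with intercurrent events unrelated to progression. Both can stand beside 7.6.7.5; only a cross-reference is missing.
- **That the primary endpoint is affected.** Section 10.1.1 defines response by RECIST or PSA, the rules in 10.3.6 count responses only, and the best-response tables in 7.6.8 have no pain entry. Responses could be lost indirectly if sites removed unchanged patients before assessment, but nothing in the documents shows that they do.

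**Conclusion.** The point holds as a defect in a stated rule. Followed exactly, Section 7.6.7.5 classes a patient on an unchanged opioid for cancer pain at a disease site as progressed, against the evident intent of the objectives. The effect is confined to objective PFS, a descriptive secondary endpoint in each cohort, and to the discontinuation condition for individual patients. No effect on the primary response rate, its power or the Simon decisions is claimed.

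The direction is downward and the size is unknown. The 45%, 40% and 35% figures assume that every baseline user is counted, that baseline use is 10%, 20% or 30%, and that it is unrelated to true progression. They show what the wording permits; they do not estimate what happened in this trial. Counting fewer users, or faster true progression among them, makes the bias smaller, and it is zero if sites already require worsening or if no patient enters on opioids.

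**What to change.** In Section 7.6.7.5, count opioid use as progression only when it is newly started, or increased over the use recorded at the screening medication review, for prostate-cancer pain at a disease site. State what counts as an increase, so that one ambiguity does not replace another. Apply the same rule in the objective-PFS derivation under 10.1.2.

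The cost is one clause and one derived baseline flag, with no new visits or tests. If dose was not recorded at screening, either count new starts only or read increases from source notes. The downside is that some true pain progression in baseline users may then be missed.

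On timing, this version is dated June 2023, while the synopsis estimated last-subject completion in April 2021, and the documents do not give accrual status. If PFS data already exist, the rule should be fixed and documented before PFS is analyzed.
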